We have designed a prospective randomized double-blind single center study on 100 patients with severe kidney failure undergoing kidney transplantation surgery. Patients will be randomized to receive either NMB with rocuronium and sugammadex for NMBR (intervention group) or NMB with rocuronium and neostigmine for NMBR (control group). Respiratory function will be objectively monitored starting in PACU and during the first 3 postoperative days or until end of monitoring criteria are met. A blinded assessor will record the frequency of hypoventilation events as well as the accumulated minutes of hypoventilation. Quantitative TOF monitoring will be evaluated by a blinded investigator. Additional data related to patient's comorbidities, morphine equivalents (mg/kg) received, validated dyspnea patient-reported scores, pulmonary complications, kidney graft relevant data and outcomes, and hospital resource utilization and estimated costs will also be collected.

After signing informed consent, patients will be randomized to receive, during kidney transplant surgery, NMB with rocuronium and NMBR with either sugammadex (intervention group) or neostigmine (control group). Both groups will receive intraoperative NMB agents and reversal medications as guided by qTOF monitoring and following FDA-approved doses (see details below). In the PACU, we will perform continuous monitoring of their MV during their PACU stay and assess qTOF at selected time points in all patients. Institutional discharge criteria from PACU is based on an Aldrete's score[33] ≥ 8 assuming there are no discharge concerns by the patient's healthcare providers (PACU nurse, anesthesiologist and/or surgeon). After discharge from PACU and during the first 3 postoperative days (or until end of monitoring criteria if sooner) we will maintain the continuous MV monitoring and daily quantitative TOF assessment, collect opioids received and data relevant to pulmonary complications, kidney graft outcomes and estimated healthcare costs. At the postoperative surgery clinic visit or by phone interview we will collect patient's subjective dyspnea scores and compare to their baseline (with a validated questionnaire), as well as updated PPCs, kidney graft outcomes, hospital resources utilization and estimated healthcare costs.

Preoperative phase

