Screening for eligibility and consenting will take place once the patient has been accepted for kidney transplantation at the University of Colorado Hospital by the Transplant Surgery team. Randomization will occur after patients consent for the study. Only the PI will remain unblinded to the group allocation (see below).

Preoperative data will be collected by the blinded investigator (study coordinator), including baseline vital signs (including room air SpO₂), comorbidities, medications, and kidney graft relevant factors. The baseline dyspnea scores will be assessed by asking patients to complete the PROMIS® v1.0 Dyspnea Functional Limitations Short Form 10a_9-2-2016 questionnaire (available at http://www.healthmeasures.net/administrator/components/com_instruments/uploads/PROMIS%20SF%20v1.0-Dyspnea%20Functional%20Limitations%2010a_9-2-2016.pdf). This is a validated and standardized short questionnaire to quantitate if sugammadex used for NMBR reduces the subjective dyspnea scores relative to baseline.

Intraoperative phase

We will perform a prospective parallel randomized study of rocuronium/sugammadex (intervention) vs. rocuronium/neostigmine (control) for NMB and NMBR at the end of kidney transplantation surgery. This will be performed by the unblinded investigator, following the following protocol(s):

- A quantitative TOF (qTOF) monitor (the Stimpod NMS450®, Xavant Technology Ltd., South Africa, the acceleromyography-based monitor available at UCH, and/or the TwitchView™, Blink Device Company, Seattle, WA, an electromyography-based monitor) will guide the NMB and NMBR management in all study patients. Quantitative NMB monitoring are considered superior to the more routinely-used but subjective qualitative TOF monitors[34, 35]. The qTOF monitor will be placed in the ulnar nerve territory to stimulate the adductor pollicis muscle[36] immediately after loss of consciousness during induction of anesthesia. The exact location of monitoring will be marked and used for qTOF measurements in the postoperative period.
- NMB brief protocol: Rocuronium will be the NMB agent used in both groups as guided by the qTOF and following standard dosing protocols in order to achieve adequate NMB to allow the intubation and surgical procedure (routinely T4/T1 < T3 until closure of surgical incision). Rocuronium dosing: 0.6-1.2 mg/kg for intubation, 0.08-0.2 mg/kg bolus for maintenance with recovery of second twitch (T2) in qTOF.

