Kidney graft outcomes, including postoperative ClCr, daily urine output, need for dialysis postoperatively, diagnosis of delayed graft function, kidney graft rejection. Postoperative hemodialysis is not usually planned and typically reserved for patients with immediate donor graft failure who exhibit signs of congestive heart failure within the first week after transplantation. The need of rescue hemodialysis within the first week after kidney transplantation is an accepted and simple definition of delayed kidney graft function[46].

Hospital resources utilization: hospital floor length of stay (LOS) (days, rounded to half a day), ICU admission and LOS, estimated cost based on average daily cost at a postoperative UCH floor or ICU and/or based on reported estimated costs per PPC[47, 48]

Hypersensitivity adverse events: hypersensitivity signs and symptoms, including but not limited to rash, bronchospasm or anaphylaxis, will be obtained for up to 3 postoperative days directly from the patient and the patient's providers. Their relationship to sugammadex will be assessed by the patient's physicians and the study safety officer. Their confirmatory testing and management will be performed strictly at the discretion of the patient's physicians.

Statistical Methods

The primary hypothesis is that the frequency of patients with one or more episodes of hypoventilation events in PACU (% of patients) is lower in the sugammadex group compared to neostigmine (controls). This will be analyzed by logistic regression which includes as covariates group allocation, total morphine equivalents, and TOF T4/T1 response, and other observed significant and clinically relevant differences between the groups. The odds ratio for the group covariate will be the primary outcome of interest, with the other covariates included in the model to adjust for potential confounders related to hypoventilation.

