The secondary analysis comparing delayed efficacy of sugammadex to neostigmine in reducing the incidence of hypoventilation during the first 3 postoperative days will assume the same model and covariates as the primary hypothesis. To compare the incidence of PPCs a logistic regression model will be used with the binary outcome of any PPC and will include covariates for group and total morphine equivalents. Hospital length of stay and costs will be compared between groups using a linear regression model including covariates for group, total morphine equivalents, presence of respiratory comorbidities and other clinical differences that may influence the outcome. Continuous outcomes may be transformed if they violate the normality assumption (e.g., a log-transformation).

Multiplicity

Given only one primary outcome and hypothesis, there is a not a concern for multiplicity. Secondary analyses are considered exploratory in this protocol.

Power/Sample Size:

Based upon a sample size of 40 patients per group, this study has 90% power to detect a 50% difference in hypoventilation incidence in the PACU (from 76% as reported in previous studies[21] to 38%, alpha 0.05), assuming a potential dropout of up to 6 patients per group. The 50% reduction is considered clinically relevant for a decrease in the frequency of hypoventilation, a precursor of more clinically significant complications such as hypoxemia, reintubation or pneumonia. Quantifying the contribution of hypoventilation into more severe complications is challenging, and details of duration and severity of hypoventilation are not well known. Thus, only a significant reduction in hypoventilation incidence (i.e. 50%) may be accepted as relevant. This trial will provide additional detailed information that may provide more insight on the clinical consequences of hypoventilation (e.g. potential association between accumulated minutes of MV <40% expMV and decrease in SpO₂/FiO₂ over the following 30 min).

A sample size of 40 patients per group would also have approximately 80% power (78%) to detect a difference in case the incidence of any hypoventilation events is 60%, instead of the literature-based 76%. The table below provides the sample size per group to achieve a variety of assumptions for the primary outcome, alpha, and power:

Incidence Group 1	Incidence Group 2	Alpha	Power	Sample Size per Group
1. 0.76	2. 0.38	3. 0.01	4. 0.8	5. 39
6. 0.76	7. 0.38	8. 0.05	9. 0.8	10. 26

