11. 0.76	12. 0.38	13. 0.01	14. 0.9	15. 48
16. 0.76	17. 0.38	18. 0.05	19. 0.9	20. 34

Although our sample size has been designed based on the frequency of hypoventilation in patients during the PACU stay, we have also estimated the power that a sample size of n=40 patients per group would have to detect a difference on the incidence of residual NMB. In a preliminary sample of 25 patients after general anesthesia and neostigmine used for NMBR at our institution, 9 patients had a quantitative TOF T4/T1 <0.9 in the PACU (36%). This matches the incidence range 10-50% of TOF <0.9 observed in other studies[8, 10, 49]. The reported frequency of qTOF <0.9 after 15min of

sugammadex administration in other surgical populations is <8%[34, 39, 50, 51]. With this incidence of residual NMB, our proposed sample size would have 90% power to detect a reduction to residual NMB to an incidence of 5% (alpha 0.05):

G. Summarize Knowledge to be Gained

This study will fill an important gap of knowledge with immediate clinical applications: 1) determine the efficacy of sugammadex, compared to neostigmine, for NMBR in patients with severe kidney dysfunction undergoing a kidney transplant; and 2) characterize the effect of sugammadex and neostigmine on postoperative ventilation, dependent and independent to residual or recurrent NMB and other contributing factors (e.g. opioids). Our study will describe the effect of NMBR on objective and quantitative assessments of qTOF and minute volume ventilation. Additional measures will include patient's subjective dyspnea scores (with a validated questionnaire), PPCs and kidney graft outcomes, hospital resource utilization and estimated healthcare costs.

H. References

- 1. Fuchs-Buder, T., R. Nemes, and D. Schmartz, *Residual neuromuscular blockade: management and impact on postoperative pulmonary outcome*. Curr Opin Anaesthesiol, 2016. **29**(6): p. 662-667.
- 2. Hayes, A.H., et al., *Postoperative residual block after intermediate-acting neuromuscular blocking drugs*. Anaesthesia, 2001. **56**(4): p. 312-8.
- 3. Fortier, L.P., et al., *The RECITE Study: A Canadian Prospective, Multicenter Study of the Incidence and Severity of Residual Neuromuscular Blockade*. Anesth Analg, 2015. **121**(2): p. 366-72.

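### The enrolment total is 100 in the design section but 80 (2 × 40, dropout included) in the power section, and the printed 90% and 78% powers use different evaluable numbers

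*Combined protocol and SAP*

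**What the plan says.** Section III.C, Study Design and Research Methods, describes a randomised, double-blind "single center study on 100 patients with severe kidney failure undergoing kidney transplantation surgery". The Preoperative phase text in III.C adds: "Randomization will occur after patients consent for the study".

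Section III.F, Power/Sample Size, uses a different number: "Based upon a sample size of 40 patients per group, this study has 90% power to detect a 50% difference in hypoventilation incidence", from 76% to 38% at alpha 0.05, "assuming a potential dropout of up to 6 patients per group". The table there gives 34 per group for that scenario at alpha 0.05 and 90% power. The next paragraph says: "A sample size of 40 patients per group would also have approximately 80% power (78%) to detect a difference in case" the incidence is 60%; the rate in the other group is not stated and dropout is not mentioned. For residual blockade the section returns to the same number ("we have also estimated the power that a sample size of n=40 patients per group would have to detect a difference") and then refers to it as the proposed sample size.

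No allocation ratio is printed. The planned primary analysis (III.F, Statistical Methods) is covariate-adjusted: "This will be analyzed by logistic regression which includes as covariates group allocation, total morphine equivalents, and TOF T4/T1 response".

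**The concern.** The same plan gives two enrolment figures, 100 and twice 40, and does not connect them. The dropout allowance is the natural bridge, but it appears to have been spent already in going from 34 to 40.

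The two powers for hypoventilation are each introduced with 40 patients per group, so a reader would take them as comparable. If one is after dropout and the other before it, the second looks better than it should beside the first. That second figure matters because it is the plan's only check on a control incidence below the literature value of 76%.

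At stake are the point at which recruitment stops and an honest statement of power in the less favourable scenario.

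**Working it through.** **Inputs.** 100 patients (III.C). From III.F: 40 per group; up to 6 dropouts per group; 76% vs 38%; alpha 0.05; table values 39, 26, 48 and 34 per group; 78% power at 60% incidence. *Assumed:* equal groups, a two-sided test, and a comparator of 30% in the 60% scenario (the same 50% reduction).

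**Step 1: identify the plan's method.** With p̄ = (p1 + p2)/2, the pooled two-proportion formula is

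n = [z(1−α/2)·√(2p̄(1−p̄)) + z(power)·√(p1(1−p1) + p2(1−p2))]² / (p1 − p2)²

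For 76% vs 38%, p̄ = 0.57, and the two square roots are 0.7001 and 0.6465.

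- alpha 0.01, power 80%: 38.2, rounded up to 39
- alpha 0.05, power 80%: 25.4, rounded up to 26
- alpha 0.01, power 90%: 48.0 (47.97), rounded up to 48
- alpha 0.05, power 90%: (1.960 × 0.7001 + 1.2816 × 0.6465)² / 0.38² = 33.5, rounded up to 34

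All four table rows reproduce.

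**Step 2: the enrolment total.**

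- 34 + 6 = 40 per group, so the allowance is inside the 40 and the total is 2 × 40 = 80.
- Adding 6 per group again: 2 × 46 = 92.
- Inflating 40 at the same rate (6/40 = 15%): 40/0.85 = 47.1, rounded up to 48, giving 96.
- Working back from 50 per group: ending at 40 means losing 10 (20%), and ending at 34 means losing 16 (32%). The plan states 6.

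No route using the stated allowance reaches 100.

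**Step 3: which evaluable number each power uses.** Solving the same formula for power:

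power = Φ{ [√n·|p1 − p2| − 1.960·√(2p̄(1−p̄))] / √(p1(1−p1) + p2(1−p2)) }

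- 76% vs 38%, n = 34: (2.216 − 1.372)/0.6465 = 1.305, power 90.4%
- 76% vs 38%, n = 40: (2.403 − 1.372)/0.6465 = 1.595, power 94.5%
- 60% vs 30%, n = 40: (1.897 − 1.379)/0.6708 = 0.773, power 78.0%
- 60% vs 30%, n = 34: (1.749 − 1.379)/0.6708 = 0.552, power 71.0%

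The printed 90% is therefore the figure at 34 per group, and the printed 78% is the figure at 40. Exact power of the uncorrected chi-square test agrees: 90.3% and 94.7% for the first pair, 79.6% and 70.4% for the second. A continuity correction (91.2%) or Fisher's test (91.7%) comes near 90% at n = 40, but these give 70.4% and 72.5% in the 60% scenario. No method tried returns both printed powers at one common n.

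**Step 4: both scenarios on a common basis** (pooled formula, two-sided 0.05, unadjusted).

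| Evaluable per group | How reached | 76% vs 38% | 60% vs 30% |
|---|---|---|---|
| 34 | 40 enrolled, 6 lost | 90.4% | 71.0% |
| 40 | 40 enrolled, none lost | 94.5% | 78.0% |
| 42–43 | 50 enrolled, 15% lost | 95–96% | 80–81% |
| 44 | 50 enrolled, 6 lost | 96.2% | 81.9% |
| 50 | 50 enrolled, none lost | 97.9% | 86.6% |

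For residual blockade (36% vs 5%) the pooled power is 90.4% even at 34 per group, so that 90% is not shown to be overstated.

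**The case against.** The strongest reply is that nothing is miscalculated. The 90% sentence mentions dropout and the 78% sentence does not, and the 34 can be read from the table, so a careful reader can recover both bases. That stands: the second part of this point is about presentation. But both figures are introduced with the same 40 per group, and only recalculation shows that they differ in basis.

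It can also be said that 71% is a worst case. Six is a maximum, and the 30% comparator is inferred. This is fair. At 80 patients the power falls gradually from 78% to 71% as dropout rises. The inference is well supported, since 30% returns 78.0% at 40 per group.

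Finally, 100 might be a ceiling that allows for attrition. Consent is taken once a patient is accepted for transplantation and randomisation follows it, so losses before surgery are possible. The plan does not say this, however. It attaches 100 to randomised patients undergoing transplantation, describes no step at which 20 would be lost, and states an allowance of 6 per group, not 10.

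The residual-blockade sentence ends in a colon, as if a table followed that was lost in the text supplied. A missing evaluable number there is not counted against the plan.

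**Conclusion.** The point holds. The two totals differ by 20 patients, and the stated dropout allowance does not bridge the gap. The printed 90% is an after-dropout power (34 per group) and the printed 78% a before-dropout power (40 per group); on the 34 basis the latter is about 71%.

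The consequence for the primary comparison is small: for an unadjusted test of 76% vs 38%, power is at least 90% at every number considered. The effect is confined to the lower-incidence scenario. With a 50% reduction, 80% power needs a neostigmine incidence of at least 66.8% at 34 per group, 61.5% at 40 and 58.5% at 44.

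These figures rest on equal groups, two-sided testing, the inferred 30% comparator and no covariate adjustment. The effect of adjustment on power cannot be computed, because the plan gives no covariate effects. Differences of 1 to 2 points between the pooled and exact methods are not meaningful.

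**What to change.** Choose one enrolment total and state it, with the allocation and the evaluable number per group, in both III.C and III.F. State the comparator for the 60% scenario. Put the evaluable number beside each power, and note that the powers are for an unadjusted two-proportion comparison while the primary analysis is adjusted logistic regression.

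- **If 100:** 50 per group, with the dropout allowance restated for 50. At 6 lost per group (44 evaluable), power is 96% for 76% vs 38% and about 82% for 60% vs 30%. At 15% lost (42–43 evaluable), it is 95–96% and 80–81%.
- **If 80:** 40 per group with up to 6 dropouts per group (at least 34 evaluable). Power is at least 90% for 76% vs 38%, and 71% to 78% for 60% vs 30%.

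The sponsor must decide which total is intended; after that the change is to wording only. No patients beyond the printed 100 are needed. Confirming 100 with either of those losses makes no stated power less favourable. Keeping 80 means replacing the single 78% with a range.
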